## RESEARCH PROTOCOL

### Specific Aims

Overactive bladder (OAB) syndrome is characterized by the symptom complex of urinary urgency, usually with associated frequency and nocturia, with or without urgency urinary incontinence in the absence of infection or other pathology [9]. OAB affects approximately 31% of women over the age of 65 [10]. Vaginal estrogen, a well-documented treatment for OAB in hypoestrogenic women, has been shown to improve symptoms of frequency, urgency and urgency urinary incontinence (UUI) [7, 11, 12]. Several theories have been proposed to explain the mechanism underlying estrogen's effect on lower urinary tract symptoms (LUTS) [13, 14]. We propose that estrogen treatment influences bacterial communities (microbiomes) in the vagina and bladder and alters urothelial and vaginal (AMPs); thereby improving OAB symptoms in hypoestrogenic women.

Long-standing medical dogma has been replaced by clear evidence that a female urinary microbiome (FUM) exists [3, 4]. Our research team recently reported that the FUM in women without OAB is less diverse than the FUM of women with OAB [3]. We soon will report that FUM status stratifies women with OAB into treatment response groups and women with less diverse FUMs are more likely to respond to anti-cholinergic OAB therapy (Thomas-White et al., in prep). This suggests that the FUM is a factor in lower urinary tract symptoms (LUTS) and that FUM diversity contributes to LUTS and treatment response, like the vaginal microbiome and its contribution to vaginal symptoms [5, 6].

In hypoestrogenic women, the vaginal microbiome shifts from low diversity communities, commonly dominated by *Lactobacillus*, to more diverse communities dominated by anaerobes [5]; this change can be reversed with estrogen treatment [6-8]. Since the FUM of women with OAB includes bacteria similar to those of the vaginal microbiome (e.g. *Lactobacillus*, *Gardnerella*, and diverse anaerobes) [3], we reason the FUM would respond similarly to estrogen and become less diverse. Although transvaginal medications likely alter nearby bacterial niches (e.g. the bladder), no study has reported the urinary microbiomic response to vaginal estrogen.

While almost nothing is known about urinary/vaginal microbiome interplay, even less is known about immune response modulation in the bladder and vagina. However, estrogen reduces the subsequent UTI rate in hypoestrogenic women affected by recurrent UTI [9, 10], and estrogen induces urothelial antimicrobial peptide (AMP) expression [15]. Since AMPs exhibit microbicidal activity, stimulate inflammation, and facilitate epithelial barrier homeostasis [11], estrogen may work through AMPs as mediators to optimize microbial equilibrium.

**We hypothesize that, following estrogen treatment of hypoestrogenic women with OAB, symptom improvement will be associated with 1) reduced FUM diversity, 2) alteration of other FUM characteristics and 3) increased AMP levels.** We propose two specific aims:

**Aim 1: To compare pelvic floor microbiome (PFM) diversity and AMP levels before and after estrogen treatment in hypoestrogenic women with OAB symptoms.**

We will enroll 20 hypoestrogenic patients with bothersome OAB prior to clinically indicated vaginal estrogen treatment as part of a pilot study. We will collect catheterized urine, voided urine, perineal swabs, vaginal swabs and vaginal lavage at baseline and 12 weeks post treatment. We will assess the associated PFMs (i.e. urinary and vaginal microbiomes) using two complementary approaches: (i) Expanded Quantitative Urine Culturing (EQUC) and/or (ii) 16S rRNA amplicon sequencing. We will quantify candidate AMPs by quantitative PCR and protein analysis [12, 13]. We will compare and contrast each PFM and its associated AMP profiles. Relevant questions include: Do associations exist amongst adjacent PFMs and between PFMs and AMPs? Do PFMs and AMPs change in response to estrogen? Does an improved (less diverse) PFM correlate with an optimized AMP profile?

**Aim 2: Determine if FUM characteristics correlate with OAB symptoms.**

At baseline and 12 weeks, we will use the overactive bladder questionnaire (OAB-q) [14] to evaluate symptoms and determine if PFM characteristics (e.g., composition, diversity, abundance, specific organisms) and AMP levels (gene expression and protein levels) correlate with patient symptoms. Relevant questions include: Does response to estrogen associate with pre-treatment PFM and/or AMP characteristics? Do PFM and/or AMP changes correlate with treatment response?

**Significance:** The medical field is beginning to adopt treatments that alter an individual's microbiome and AMP profile to improve patient health; however, this approach has not been adopted for LUTS treatment. Here, we propose the first step in development of such a therapy. If our hypothesis is correct, we could validate estrogens a first line of treatment in hypoestrogenic women. It could also propel the use of an individual's PFM and/or AMP characteristics to develop future personalized therapies to improve treatment response and/or prevent LUTS.

[figure not shown]
**Estrogen improves OAB symptoms:** There is compelling evidence to suggest that vaginal estrogen therapy relieves symptoms of OAB including frequency, urgency and UUI in postmenopausal women [7, 8, 11, 12]. The evidence is sufficient to list the application of vaginal estrogen alone as a treatment option for OAB in the clinical practice guidelines for postmenopausal women with urogynecological complaints [18]. The mechanism of vaginal estrogen's effect on OAB symptoms is poorly understood. Vaginal estrogen has the ability to modify the vaginal microbiome and reduce recurrent urinary tract infections in postmenopausal women [16]. We reason that vaginally applied estrogen would also modify the FUM, which appears to play a role in OAB [1].

**The Bladder is Not Sterile.** Current treatments and preventive strategies are based upon the dogma that the bladder is a sterile environment. Compelling new evidence challenges this long-held belief. Detection of bacterial DNA and isolation of live bacteria from urine taken directly from the bladders of women with and without urinary symptoms has been reported by us [1-3], and by others [4, 5]. However, the role of the female urinary microbiome (FUM) in urinary health and disease is incompletely understood.

**FUM diversity correlates with symptoms.** Recently, we sequenced and cultured urines from individuals with urgency urinary incontinence (UUI) and continent controls using two complementary methods, 16S rRNA sequencing and expanded quantitative urine culturing (EQUC) [1]. We observed a striking difference in the diversity between the two cohorts (**Figure 1**). Continent controls had a markedly less diverse FUM than did the UUI cohort (1 [interquartile range (IQR) = 1 to 2] versus 3 [IQR = 1-7],  $p=0.0001$ ). This suggests that a healthy FUM is a less diverse FUM. By decreasing FUM diversity, we might be able to improve patient symptoms.

**Vaginal and bladder microbiomes are similar.** The vaginal microbiome is characterized by five dominant genera or species; these groups are called community state types (CSTs). Four of the five CSTs are low diversity microbiomes dominated by different *Lactobacillus* species, making *Lactobacillus* the most commonly found organism in the vagina. The final CST (CST IV) is a diverse mixed community dominated by anaerobes such as *Gardnerella*, *Prevotella*, and *Aerococcus* [19]. The organisms found in the bladder tell a very similar story. The FUM of the majority of individuals is dominated by *Lactobacillus*, with another group dominated by one or more anaerobes, such as *Gardnerella*, *Prevotella*, and *Aerococcus* [1]. This similarity in bacterial composition and the anatomical proximity of these two biological niches, lead us to reason that bacteria of bladder and vagina might behave similarly. A major factor in determining the health of the vaginal microbiota is estrogen.

**Fig 1: UUI communities are more diverse than non-UUI controls.** A rarefaction analysis showing the number of unique species of bacteria isolated (using EQUC) with each new patient sampled. More unique species of bacteria are seen in the UUI population than the non-UUI controls.

**Diversity of the vaginal microbiome changes in response to estrogen.** The majority of healthy premenopausal women have low diversity vaginal microbiomes dominated by *Lactobacillus* [19]. A small percentage of women have a higher diversity microbiome dominated by anaerobes [19]. Following menopause, many women lose *Lactobacillus* and their vaginal microbiomes become more diverse and anaerobic. However, this change can be reversed with estrogen treatment. Since the vagina and bladder have

similar organisms, we anticipate that estrogen would alter the FUM as it does the vaginal microbiome, reducing its diversity. Since high FUM diversity correlates with UUI and low FUM diversity with a lack of UUI, we reason that estrogen treatment will improve LUTS.

## Methodology

**Power Calculation/Sample Size:** Based on the difference in diversity between UUI and non-UI controls (Fig 1), we were able to do a power analysis and determine that a sample size of 60 will give us sufficient power (0.816), using the Wilcoxon-Mann-Whitney test, to detect the difference between patients whose urinary microbiomes retain high diversity compared to those that change to a low diversity state. Initially, we plan to conduct a pilot study of 20 patients to inform a future, larger funded study.

**Recruitment:** Women will be recruited from the ambulatory urogynecology clinic at Loyola University Medical Center. A total of 60 hypoestrogenic, post-menopausal women will be enrolled as part of a pilot study. The PFM and AMPs will be measured prior to, and following 12 weeks of, vaginal estrogen treatment. Each patient will act as her own control, with her own baseline prior to estrogen treatment. Subjects who meet eligibility criteria and agree to research participation will indicate their consent by signing the research consent form. Subjects will indicate their consent for biorepository storage of leftover urine for potential future IRB-approved studies by signing the biorepository consent form. Consistent with prevalent research regulations and policies, a signed copy of the research and biorepository consent documents will be given to the subject and the investigator will keep the original research consent documents. Participation in the research will not depend upon participation in the biorepository (**Appendix 1**). Please see the ethics and patient consent section for details of the consent process.

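### Enrolment is given as both 20 and 60, and the only power figure (0.816 at 60) is for a two-group rank comparison that the analysis plan does not contain

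*Combined protocol and SAP*

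**What the plan says.** **Enrolment.** Specific Aims, Aim 1: "We will enroll 20 hypoestrogenic patients with bothersome OAB", and this is to happen "prior to clinically indicated vaginal estrogen treatment as part of a pilot study". Methodology, Power Calculation/Sample Size, agrees: "Initially, we plan to conduct a pilot study of 20 patients to inform a future, larger funded study". The next paragraph, Recruitment, does not: "A total of 60 hypoestrogenic, post-menopausal women will be enrolled as part of a pilot study".

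**Power.** The power paragraph takes its effect from the earlier cross-sectional difference between women with urgency incontinence and continent controls. It states that "a sample size of 60 will give us sufficient power (0.816), using the Wilcoxon-Mann-Whitney test". The contrast it names is between women whose bladder microbiome stays diverse and women who move to low diversity. It does not give the expected split between the two groups, the sidedness, or whether 60 is a total or a number per group.

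**Design and analysis.** Recruitment says: "Each patient will act as her own control, with her own baseline prior to estrogen treatment". The Statistical Analysis Plan fits a separate linear mixed-effects regression to each diversity measure. The terms are time, OAB-q symptom severity, physical therapy, weeks of estrogen compliance and body mass index, with a random intercept per woman. Its only Wilcoxon test is the signed-rank test, applied to the OAB-q.

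**The concern.** A power figure belongs to one test, one contrast and one sample size. Here the test and the contrast are missing from the analysis plan, and the sample size is one of two that the protocol gives for itself.

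Three things are at stake. A null result for diversity could be read as coming from a study with 82% power, which nothing in the plan establishes. The later, larger study could be sized from a two-group test although its analysis may be before-after. And a reader cannot tell whether 0.816 describes this study or the later one.

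**Working it through.** **1. Can 0.816 be reproduced?** The plan gives N = 60 and the Wilcoxon-Mann-Whitney test, and Expectations gives a 0.05 significance level. Two-sidedness is assumed here. With asymptotic relative efficiency 3/π, the standardised difference that gives power 0.816 is approximately

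d = (1.960 + 0.900) / √[(3/π) · n₁n₂/(n₁+n₂)].

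For 30 v 30 this is 2.860 / √(0.955 × 15) = 0.756. The noncentral t version gives 0.769. By the noncentral t method:

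| Split | d needed for 0.816 |
|---|---|
| 30 v 30 | 0.77 |
| 20 v 40 | 0.82 |
| 10 v 50 | 1.03 |
| 60 per group | 0.54 |

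The only effect figures in the document (section on FUM diversity and symptoms) are a median of 1 (IQR 1 to 2) in controls against 3 (IQR 1 to 7) in the urgency incontinence group. Simulated species counts shaped to these medians and IQRs give a power of 0.72 to 0.97 at 30 v 30, two-sided, depending on the assumed tails. One of the shapes gives about 0.82. So 0.816 is plausible for the stated contrast, and it can be neither confirmed nor refuted.

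**2. Does it carry over to the planned analysis?** Side by side:

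| | Power paragraph | Statistical Analysis Plan |
|---|---|---|
| Comparison | Between two groups of women | Within woman, baseline to 12 weeks |
| Groups | Stays diverse v becomes less diverse | None |
| Method | Wilcoxon-Mann-Whitney | Linear mixed model, random intercept, covariates |
| Spread that sets the power | Between-woman | SD of within-woman change, or pre-post correlation |

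The last entry is given nowhere. Expectations also anticipates a smaller difference than in the earlier study and does not say how much smaller.

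**3. Why the direction is unknown.** As an illustration only, take a mean fall from 3 to 1 species and an SD of 6/1.349 = 4.45 at both visits. Assume a pre-post correlation r from 0 to 0.7. The SD of the change is 4.45·√[2(1−r)]. It runs from 6.29 (r = 0) to 3.45 (r = 0.7), so the fall of 2 is 0.32 to 0.58 SD of the change. A paired t-test with 60 pairs then has a power of 0.68 to 0.99, on either side of 0.816. With 20 pairs it has 0.27 to 0.69. With half that fall, the ranges are 0.23 to 0.60 and 0.10 to 0.23.

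**4. What the 20 v 60 question is worth.** Possible Limitations expects about 7% loss: 60 × 0.93 = 55.8, about 56 evaluable; 20 × 0.93 = 18.6, so 18 to 19. For an unadjusted paired t-test, solve P[T′(n−1, δ√n) > t(0.975, n−1)] = 0.80 for δ, the mean change in SDs of the change:

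| Evaluable pairs | δ at 80% power, two-sided 0.05 |
|---|---|
| 56 | 0.381 |
| 19 | 0.680 |
| 18 | 0.701 |

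The smaller study needs a change about 1.8 times as large (0.680/0.381 = 1.78; 0.701/0.381 = 1.84). This is a stand-in for the mixed model's time effect, which can have lower power when a covariate such as OAB-q severity itself shifts between visits.

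**The case against.** The strongest reply is that the 20-patient sentence directly follows the power sentence. On that reading 60 is the target of the later funded study, whose analysis plan is not in this document, and the mismatch of tests is not an error in this plan. This stands as far as it goes, and it is why the mismatch is stated conditionally. It does not settle the matter, because Recruitment says that 60 will be enrolled and calls that a pilot too.

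It is also fair to say that a pilot needs no power calculation and that a paired design may be more efficient than a two-group one. Both are true. But the plan does claim sufficient power, and efficiency depends on a correlation it does not give.

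Three stronger readings are tempting, and the documents support none of them:

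- *0.816 is miscalculated.* The split, the sidedness and the meaning of 60 are unstated, and plausible inputs reproduce the figure.
- *60 women are too few.* Without an SD of change, the power of the planned analysis could be higher or lower than 0.816.
- *Covariate adjustment costs a definite amount of power.* The documents give no OAB-q change, SD or correlation. A change-score regression with assumed inputs would also overstate the loss for a random-intercept model, which uses between-woman information as well.

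**Conclusion.** The point holds in conditional form and should be fixed. The enrolment contradiction is plain on the text and is the firmer defect. Given that contradiction, 0.816 fails on either reading: with 60 women it describes a test and grouping outside the analysis plan, and with 20 it describes another sample size. The power of the planned diversity analysis is not identified.

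The detectable changes of about 0.38 SD (56 evaluable) and 0.68 to 0.70 SD (19 to 18 evaluable) assume an unadjusted paired t-test, two-sided 0.05, 80% power and the protocol's 7% loss. They show what hangs on the choice between 20 and 60; they are not the power of the mixed model. No planned estimate or test changes.

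**What to change.** 1. State one enrolment number in Aim 1, the power paragraph and Recruitment, and say which study the power statement covers.
2. Remove 0.816 as the power of this study's diversity analysis. Alternatively, label it as the rationale for the later, larger study and state the expected split, the sidedness and whether 60 is a total or per group.
3. Preferably add: *This pilot is exploratory and is not powered for a diversity hypothesis.*
4. Optionally add a precision guide, labelled as an unadjusted paired approximation and not the planned model: *With 56 evaluable of 60 enrolled [or 19 to 18 of 20], such a comparison has 80% power at two-sided 0.05 for a mean change of about 0.38 SD [or 0.68 to 0.70 SD] of the change. The SD of the change is unknown, and the covariate-adjusted time effect can have lower power.* Give no numerical detectable change for the adjusted model until its inputs are known.

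The cost is a reworded sample-size paragraph and one consistent number. No extra patients and no change to the analysis are needed.

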**Expectations:** Since the FUM is more diverse in women with UII than in women without UII, since the bacteria of the FUM are similar to those of the vagina, and since estrogen treatment can reverse the increased diversity of the vaginal microbiome associated with menopause, we predict that estrogen treatment will make the FUM less diverse and improve LUTS. On the basis of our recently published study [1], we expect that hypoestrogenic women with UII, on average, will have 3 different bacterial species as detected by EQUC. We predict that estrogen treatment will reduce this average number towards the average of 1 bacterial species as detected by EQUC in the continent controls from our previous study [1]. In that study, the difference between women with UII and women without UII was highly significant ( $p=0.0001$ ). In the proposed study, we anticipate a smaller difference (since all women will have UII) and will consider significance at  $p<0.05$ . Since 16S sequencing and EQUC provide complementary views of the FUM [1], we anticipate that sequencing will provide similar results; however, sequencing can identify bacteria that are not cultured, even by EQUC, and thus will provide us with a broader view of FUM composition. We predict that AMP levels will correlate with certain microbiota profiles, and anticipate that increased AMPs *via* estrogen supplementation will correlate with improved frequency and severity of OAB symptoms.

**Possible Limitations to the study:** We do not anticipate any problems recruiting and retaining patients, as we have a long track record of similar studies. We anticipate some loss to follow-up (~7%). The timing of the first sample, taken at the first visit, will be necessarily variable but will be about 12 weeks from the commencement of estrogen treatment.

We do not anticipate any problems in the transfer of samples from the Ambulatory Clinic to the Clinical Microbiology Lab or the Genomics Facility, respectively, for culture and sequencing, as we have an established

and successful protocol for such transfer. For similar reasons, we also do not anticipate problems with the culture or sequence analyses.

We know that some urinary bacteria do not grow, even under EQUIC conditions. We also know that some bacteria are not readily sequenced. However, the strengths and weaknesses of EQUIC and sequencing are complementary and thus permit a broad and relatively unbiased view of the bacterial composition of the FUM.

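### The stated power of 0.816 is tied to 60 women and 60 are enrolled, with no allowance for the plan's own 7% loss; at the same effect, about 56 evaluable women give power of about 0.79

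*Combined protocol and SAP*

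**What the plan says.** Under Methodology, the Power Calculation/Sample Size paragraph states that "a sample size of 60 will give us sufficient power (0.816"), using a Wilcoxon-Mann-Whitney test. The contrast is "to detect the difference between patients whose urinary microbiomes retain high diversity compared to those that change to a low diversity state". The effect is described only by its source: "Based on the difference in diversity between UUI and non-UI controls (Fig 1").

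The Recruitment paragraph that follows uses the same number for enrolment: "A total of 60 hypoestrogenic, post-menopausal women will be enrolled as part of a pilot study". Under Possible Limitations to the study the plan says "We anticipate some loss to follow-up (~7"%). No passage raises enrolment to cover that loss.

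A second enrolment figure also appears. The power paragraph ends "Initially, we plan to conduct a pilot study of 20 patients to inform a future, larger funded study", and Aim 1 under Specific Aims likewise speaks of enrolling 20.

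The only diversity figures given are species counts by expanded culture from an earlier study, continent controls against women with urgency urinary incontinence (UUI): "1 [interquartile range (IQR) = 1 to 2] versus 3 [IQR = 1-7"].

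**The concern.** One number serves as both the sample size behind the power figure and the number enrolled, although the plan expects to lose some women. The powered comparison makes this matter. A woman can be said to have stayed at high diversity or moved to low diversity only if she has both a baseline and a 12-week specimen. A woman lost before Visit 2 adds nothing to the contrast.

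If 60 is the number the calculation needs, the plan quotes a power, to three decimals and described as sufficient, that its enrolment will not give. Readers of a null result would judge it against 0.816. The gap is much larger if the enrolment is really 20.

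**Working it through.** **Inputs from the documents.** N = 60, power 0.816, and the Wilcoxon-Mann-Whitney test (Power Calculation/Sample Size); 60 enrolled (Recruitment); 20 enrolled (Aim 1 and Power Calculation/Sample Size); loss of about 7% (Possible Limitations to the study); significance at 0.05 (Expectations).

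**Assumptions, not in the documents.** The 60 means women analysed. The test is two-sided; a one-sided version is shown as a check. The effect and the group split stay as they were in the sponsor's calculation.

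**Step 1: can 0.816 be reproduced?** Only roughly. The plan gives no effect size, standard deviation, split or sidedness. Take each mean as the sum of the three quartiles divided by 3, and each SD as IQR/1.35:
- Controls: mean 4/3, SD 1/1.35 = 0.741.
- UUI: mean 11/3, SD 6/1.35 = 4.444.
- Difference 7/3 = 2.333; pooled SD = sqrt((0.741² + 4.444²)/2) = 3.186.
- With 30 per group: 2.333 / (3.186 x sqrt(2/30)) = 2.836; 2.836 - 1.960 = 0.876; power = 0.810.

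Simulated two-sided rank-sum tests at 30 v 30, on nine pairs of count distributions chosen to match the published quartiles (one only approximately), gave power from 0.74 to 0.92. So 0.816 is plausible but neither confirmed nor refuted. The next steps take it as given.

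**Step 2: scaling to the evaluable number.** In the usual approximation, power = Φ(λ - z), with λ = sqrt(12 c(1 - c)N) x |p - 0.5|. Here c is the share in one group and p is the probability that a woman in one group exceeds a woman in the other. With c and p unchanged, λ scales with sqrt(N), so the result does not depend on what the split was.
- At N = 60: λ = 1.960 + 0.900 = 2.860.
- Evaluable: 60 x 0.93 = 55.8, about 56.
- At 55.8: 2.860 x sqrt(0.93) = 2.758; 2.758 - 1.960 = 0.798; power = 0.788.
- At 56: 2.860 x sqrt(56/60) = 2.763; 2.763 - 1.960 = 0.803; power = 0.789.
- One-sided at 56: λ at 60 is 1.645 + 0.900 = 2.545; 2.545 x 0.966 = 2.459; 2.459 - 1.645 = 0.814; power = 0.792.

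**Step 3: enrolment that would leave 60 evaluable.** 60 / 0.93 = 64.5, so 65.

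**Step 4: the other enrolment figure.** At N = 20, two-sided: 2.860 x sqrt(20/60) = 1.651; 1.651 - 1.960 = -0.309; power = 0.38, before any loss.

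| Women contributing | Power, same effect, two-sided 0.05 |
|---|---|
| 60 (as stated) | 0.816 |
| 56 (60 enrolled, 7% lost) | 0.79 |
| 20 (pilot figure, no loss) | 0.38 |

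**The case against.** Four points can be made for the plan.

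*The plan never says that 60 means women analysed.* True. If the sponsor's calculation already allowed for loss, 0.816 could be correct for 60 enrolled. Nothing in the documents says so, and a power figure attached to a sample size is ordinarily read as women contributing data. The reading remains an inference and is labelled as one.

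*The loss is under 3 percentage points in a self-described pilot.* This stands, and it limits the weight of the point. It is a correction to a stated figure and no threat to the study.

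*The 60 may belong to the future, larger study.* This is possible, because the power paragraph and Aim 1 both speak of 20. But Recruitment enrols 60 in this study and calls it the pilot. The conflict is the plan's own, so any restated power has to be given together with the resolved enrolment.

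*Power might be much worse than 0.79.* A reader might infer this from the UUI lower quartile of 1 species ("versus 3 [IQR = 1-7"]). On that reading at least a quarter of women start at low diversity, fit neither group, and leave about 42 contributors (55.8 x 0.75 = 41.9) and power near 0.67. The documents do not support this:
- The figure cuts the number of women but holds the effect fixed. Removing women with 1 species or fewer leaves a high-diversity group that starts at 2 species, which widens the contrast. In simulations with 42 women, p rose from about 0.69-0.73 to 0.88-0.96 and power was about 0.90 or more, even at a 5 v 37 split.
- Groups defined by diversity and then compared on diversity also separate partly by construction.
- The quartile comes from an earlier UUI cohort, whereas this study admits overactive bladder with or without UUI. The share already low here is unknown.
- One species is described under Expectations as a level the group average should move towards. It is not a cut-off for individual women.

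**Conclusion.** The concern holds for attrition only. If 60 is the number the calculation requires, 60 enrolled with about 7% lost leaves about 56 evaluable women, and power at the sponsor's own effect is about 0.79 instead of 0.816. This rests on reading 60 as women analysed, on an unchanged effect and split, and on a two-sided 0.05 test; one-sided testing gives almost the same answer. The value of 0.79 inherits whatever effect lies behind 0.816 and is no independent confirmation of it.

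The conflict between 20 and 60 matters more in size, since 20 women give about 0.38 at the same effect.

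Beyond that, the documents support only a statement about what is missing. The low-diversity cut-off, the assumed split between the two groups and the handling of women already low at baseline are not given, so 0.816 for the stated contrast cannot be verified. They do not show that a known share of women falls outside the comparison, or that power is lower for that reason. The point is minor to moderate and worth correcting because the correction costs almost nothing.

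**What to change.** 1. In Power Calculation/Sample Size, say whether 60 is enrolled or evaluable. If it is evaluable, restate the power as approximately 0.79 for about 56 evaluable of 60 enrolled. No added enrolment is needed for this; a sponsor who wishes to keep 0.816 would have to enrol 65. If the calculation already allowed for loss, say so.
2. Reconcile 60 with the 20 in Aim 1 and in the power paragraph. Give the power for the number actually enrolled in this study, noting that 20 women give about 0.38 at the same effect, or state that the power figure belongs to the later study.
3. Add the inputs that would let a reader check the figure: effect size, sidedness, assumed split, the cut-off for low diversity, and how women already low at baseline are treated. Call the power approximate.

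The cost is a few sentences of sample-size wording and a slightly less favourable stated power. Unless the sponsor chooses to enrol more women, procedures, specimens and analyses are unaffected.

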Statistical analyses of the microbiome data (EQUC and 16S rRNA) will be performed using SAS software version 9.4. Descriptive statistics for demographics, clinical characteristics, and microbiome data will be calculated including means with standard deviations, medians with interquartile ranges, or counts and percentages. Medians and interquartile ranges will be presented for OAB-q subscales at each time point as well as a change score, and Wilcoxon signed-rank tests assessed statistical significance of change in OAB-q. Each diversity measure will be modeled as a separate dependent variable in a linear mixed-effects regression, with independent variables including time, OAB-q symptom severity, physical therapy completed, weeks of estrogen compliance, and body mass index, and random intercepts for subjects. Spearman's rho will be calculated for change in Lactobacillus levels associated with change in the OAB-q symptom severity (12-week minus baseline values). For AMP data analyses, Spearman's rho will be used to test associations between change in relative abundance and change in area of bacterial growth inhibition.

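### The protocol sets this pilot at 20 women in two places and 60 in a third, and the only power figure belongs to 60

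*Combined protocol and SAP*

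**What the plan says.** Three current statements give the size of the study, and each calls it a pilot.

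- Specific Aims, Aim 1: "We will enroll 20 hypoestrogenic patients with bothersome OAB prior to clinically indicated vaginal estrogen treatment as part of a pilot study".
- Methodology, Power Calculation/Sample Size: "Initially, we plan to conduct a pilot study of 20 patients to inform a future, larger funded study".
- Methodology, Recruitment, the next paragraph: "A total of 60 hypoestrogenic, post-menopausal women will be enrolled as part of a pilot study".

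The power paragraph also says that "a sample size of 60 will give us sufficient power (0.816), using the Wilcoxon-Mann-Whitney test", with the purpose "to detect the difference between patients whose urinary microbiomes retain high diversity compared to those that change to a low diversity state". No power or precision is given for 20.

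The Statistical Analysis Plan paragraph gives no enrolment number. The paragraph on possible limitations expects about 7% loss to follow-up but does not attach it to 20 or to 60.

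**The concern.** The numbers conflict as written: under the same label, Recruitment enrols three times as many women as the other two places. The conflict carries over to the power statement. If this study has 60 women, 0.816 may describe it. If it has 20, the figure belongs to a later study and this protocol has no power or precision statement of its own, although the Expectations paragraph still intends to judge significance at p<0.05. Anyone who approves, runs or reports the study needs one target to compare with what was done.

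**Working it through.** **The text.** Aim 1 gives 20, the power paragraph gives 20 for the pilot, and Recruitment gives 60 for the pilot. No passage describes the 20 as a first stage of the 60, an expansion rule or a revised target. The contradiction rests on this comparison alone; the arithmetic below only measures how much depends on it.

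**Can 0.816 be reproduced?** Not uniquely. The plan gives medians and interquartile ranges for the earlier cohorts (1, IQR 1 to 2, against 3, IQR 1 to 7), but no group split, full distributions or sidedness. Simulated Wilcoxon-Mann-Whitney tests on counts matching those quartiles, at 30 v 30 and two-sided 0.05, give 0.78 to 0.90 depending on the assumed tails. A normal approximation with SD = IQR/1.349 gives 0.62 to 0.68 two-sided and 0.73 to 0.78 one-sided. So 0.816 is plausible but cannot be verified.

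**Power at 20, given 0.816 at 60.** Assume two-sided 0.05 and the same effect and split at both sizes. The noncentrality at 60 is 1.960 + z(0.816) = 1.960 + 0.900 = 2.860. Power at N is Φ(2.860 × √(N/60) − 1.960).

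| N | 2.860 × √(N/60) | Power |
|---|---|---|
| 60 | 2.860 | 0.816 |
| 56 | 2.763 | 0.789 |
| 55 | 2.738 | 0.782 |
| 20 | 1.651 | 0.379 |
| 19 | 1.610 | 0.363 |
| 18 | 1.567 | 0.347 |

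The rows below 60 and below 20 reflect 7% loss: 60 × 0.93 = 55.8 and 20 × 0.93 = 18.6.

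Other routes to power at 20:

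- Simulated normal shift, set to give about 0.816 at 60: 0.33 at 10/10, 0.35 at 7/13, 0.33 at 5/15.
- Simulated counts with the stated quartiles, 10 v 10: 0.33 to 0.43.
- The formula above, one-sided: 0.43.
- Across all count-based and one-sided variants tried: roughly 0.24 to 0.43.

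**Precision of the analyses in the Statistical Analysis Plan.** That paragraph plans signed-rank tests for OAB-q change and Spearman correlations of changes. Methods:

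- Detectable change: one-sample t power with sample size multiplied by the signed-rank efficiency 3/π.
- Detectable rho: tanh[(1.960 + 0.842) × √(1.06/(n − 3))].
- Half-width for mean change: t(0.975, n − 1)/√n, in SD units.
- Half-width for rho near 0: tanh[1.960 × √(1.06/(n − 3))].

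| Quantity | n = 20 | n = 60 | Ratio |
|---|---|---|---|
| Detectable change, 80% power (SD of change) | 0.68 | 0.38 | 1.8 |
| Detectable rho, 80% power | 0.60 | 0.36 | 1.7 |
| 95% CI half-width, mean change (SD) | 0.47 | 0.26 | 1.8 |
| 95% CI half-width, rho near 0 | 0.45 | 0.26 | 1.7 |

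After 7% loss the detectable change is 0.70 to 0.72 SD against 0.39, and the detectable rho is 0.62 to 0.63 against 0.38.

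**Enrolment needed for a given number of pairs.** 20/0.93 = 21.5, so about 22; 60/0.93 = 64.5, so about 65.

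**The case against.** The best defence is a staged reading: the power paragraph begins its sentence on the 20 with an adverb of sequence and Recruitment speaks of a total, so the 20 could be the first part of the 60. On that reading both numbers could stand. It does not fit the text. The 20 are meant to inform a separate future study, while Recruitment calls the 60 women themselves the pilot, and no staging is described. Since the reading cannot be excluded as an intention, the fix allows for it.

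Three further objections have some force:

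- A pilot need not be powered, so the absence of a power figure for 20 is not a fault in itself. The fault is that a reader cannot tell which study 0.816 describes.
- The Statistical Analysis Plan lists no Wilcoxon-Mann-Whitney comparison. Its diversity analysis reads "Each diversity measure will be modeled as a separate dependent variable in a linear mixed-effects regression". The 0.38 is therefore the power of the test named in the power paragraph, not of a listed analysis. That mismatch is a separate matter, and the precision table covers the signed-rank and correlation analyses instead.
- The 7% loss is minor beside 20 against 60: at 60 it moves power only from 0.816 to about 0.79.

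None of these removes the contradiction.

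**Conclusion.** The concern holds. The enrolment number is stated as 20 twice and as 60 once for the same pilot, and nothing reconciles them. The documents do not show which is intended.

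The consequence is large under any reasonable assumption: power of 0.816 at 60 corresponds to about 0.38 at 20, with a range of roughly 0.24 to 0.43, and estimates are about 1.7 to 1.8 times less precise. The power figures are conditional on the unverified 0.816, the same effect and roughly the same split at both sizes; the central value also assumes a two-sided 0.05 test. The contradiction does not depend on them. It must be corrected, because the sample size and its power statement are figures on which the study relies.

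**What to change.** State the one intended enrolment number in Aim 1, Power Calculation and Recruitment, and say whether it is before or after the expected loss.

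- **If 20:** correct Recruitment, assign the 0.816 statement explicitly to the future study, and report changes and correlations as estimates with 95% confidence intervals.
- **If 60:** remove both statements of 20. Keep 0.816 only as the power of the subgroup comparison it describes (about 0.79 if 60 is before loss), not as power for the before-after mixed model.
- **If the 20 are the first part of the 60:** say so, and say whether they will be tested separately.

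The cost is wording in three places if the chosen number is the one already intended and approved. If 20 is the operative number and 60 is chosen instead, the cost is 40 more women, each with two sampling visits and a supplied three-month course of study treatment.
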